7.4.2.2 Key Secondary Endpoint of Adjudicated CMV-Specific Antiviral Therapy

Subjects' CMV-specific antiviral therapy (AVT) use will be adjudicated by the independent and blinded committee. This endpoint will be evaluated through 1 year post-transplant (i.e., through day 380 from transplantation) and will be considered as a key secondary efficacy endpoint. This endpoint will be analyzed by 2 statistical methods for FAS, mFAS and PPS-FAS.

A Cox proportional subdistributional hazards model will be used for time-to-first use of CMV-specific AVT through 1 year post-transplant. This model accounts for the competing risk of death, after which use of CMV-specific AVT can no longer be observed. If a subject used CMV-specific AVT more than once, the day of first use will be counted. If a subject did not use any CMV-specific AVT, the subject will be censored on the day of last study evaluation according to the end of study eCRF.

To evaluate the treatment effect compared to placebo, 1-Hazard Ratio, its 95% CI and p-value from the Cox model (as in Section 7.4.2.1) will be calculated.

CIFs will be used to estimate the crude incidence of CMV-specific AVT while accounting for the competing risk of death.

Additionally, the same CMH method as in the primary endpoint will be used to calculate odds ratio and its 95% CI and 1-relative risk and its 95% CI. The p-value from this method will also be calculated.

7.4.2.3 Other Secondary Endpoints

7.4.2.3.1 CMV viremia and CMV-specific AVT Use

A composite endpoint of CMV viremia and CMV-specific AVT use per the adjudication committee will be analyzed as an additional secondary efficacy endpoint for FAS and mFAS analysis sets. The CMV viremia will be based on the protocol defined definition with plasma viral load ≥ 1000 IU/mL assessed by the central laboratory. Data that is observed through day 380 from transplantation will be included.

This endpoint will be analyzed using the same CMH method as in the primary endpoint.

7.4.2.3.2 Time to CMV-specific Antiviral Therapy or End Organ Disease

A composite endpoint of time to first event between CMV-specific Antiviral Therapy (AVT) use and CMV End Organ Disease (EOD) through 1 year post-transplant (i.e., through day 380 from transplantation) will be analyzed for FAS and mFAS. Both CMV-specific AVT use

and CMV EOD will be based on the assessment of the adjudication committee. A subject without any event will be censored on the last study evaluation according to the end of study eCRF. A subject who dies prior to reporting CMV-specific AVT or EOD will be handled using a competing risks model.

This endpoint will be analyzed using the Cox proportional subdistributional hazards model and CIFs (to account for the competing risk of death) and CMH method, as described above for the key secondary endpoints.

7.4.2.3.3 All-Cause Mortality

All-cause mortality will be analyzed by incidence and/or time to event approach for FAS and mFAS by treatment group.

All-cause mortality through 1-year post-transplantation summary will include all deaths and unknown survival status. For the known deaths, the adjudication committee assessed results will be summarized for the following category: Mortality due to the subject's primary disease, and Mortality due to causes unrelated to the subject's primary disease.

All-cause mortality will be analyzed by 2 methods: time to event and the CMH method, as described for the primary analysis. For the time to event analysis, a subject with unknown survival status will be censored on the last day known alive. For the CMH analysis, subjects with unknown survival status by day 365 will be counted as dead.

7.4.3 Exploratory Endpoints

The analyses of all exploratory endpoints will be performed on the FAS and mFAS analysis sets. All endpoints derived from subjects' visits will take an analysis window through day 380 from transplantation day while the mortality will be counted up to day 365.

7.4.3.1 Analyses of Clinical Outcomes Exploratory Endpoints

The following exploratory endpoints will be analyzed by incidence and/or time to event approach by treatment group.

For the endpoint of adjudicated CMV EOD, and Investigator-reported CMV EOD, the summary will include incidence (i.e., number of episodes) where all events are added in addition to the number and percentage of subjects with at least one event. The proportion of subjects with an event will be analyzed by the CMH method and the odds ratio, its 95% CI and p-value will be calculated.

- Composite endpoint of all-cause mortality and adjudicated CMV EOD at 6 months post-transplant, using the same CMH approach as the primary endpoint. Deaths occurring up to day 180 from transplant will be counted. In other words deaths occurring on or before 180 days after transplant will be counted, although the death could be reported later. Patients with CMV EOD that is assessed by the independent and blinded adjudication committee will be counted for the events that are observed up to day 190 from transplantation.

- All-cause mortality at 6 months post-transplant using time to event method, as described in Section 7.4.1.2. Deaths occurring up to day 180 from transplant will be counted. In other words deaths occurring on or before 180 days after transplant will be counted, although the death could be reported later.
- Relapse mortality (death due to relapse of the subject's primary disease), using the same CMH approach as the primary endpoint.
- Non-relapse mortality (death due to causes unrelated to the subject's primary disease), using the same CMH approach as the primary endpoint.

The proportion and number of subjects the events below will be descriptively summarized.

- Proportion of grade 3-4 aGVHD
- Proportion of engraftment (Yes/No)
- Proportion of graft rejection/poor graft function
- Proportion of relapse of primary disease requiring therapy

Additionally, number (percentage) of subjects by taking the maximum grade of aGVHD will be summarized.

Karnofsky Performance Scale (KPS) scores are collected at baseline and post-baseline. KPS scores will be descriptively summarized at baseline and the visits specified in schedule of assessments (Table 1), but KPS scores at any additional visits will only be listed.

The endpoint of grade 3 infections other than CMV will be summarized by the incidence counting all the events and number (percentage) of subjects. The number of subjects will be analyzed by the CMH method and the odds ratio, its 95% CI and the p-value will be calculated.

7.4.3.1.1 Association of CMV Viremia and Mortality

To estimate the association between CMV viremia and mortality, subjects in each treatment group will be cross-tabulated by viremia or no viremia within 1 year post-transplant, and by alive or dead at 1 year post-transplant. In addition, a multivariable Cox proportional hazards model will be constructed in a time-dependent manner. The model will be adjusted for the factors used to stratify the randomization. CMV viremia will be treated as a time-dependent variable, starting at the time of the first occurrence of protocol-defined CMV viremia. The model for this analysis will include, in addition to CMV viremia, all the factors included in the final Cox regression model described earlier in this subsection.

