### **2.2.2 Dose Rationale**

Efficacy and safety data was collected from normal healthy subjects in a phase 1 trial as well as HCT recipients in a phase 2 clinical trial (VCL-CB01-101 and CB01-202, respectively). The dose used in the phase 2 study was 1 mL of 5 mg/mL and 4 doses were given over approximately a 6 month time period. The dose and dose schedule appeared to be well tolerated.

The first dose of vaccine is scheduled to be administered at -14 to -3 days prior to transplant, and within 72 hours prior to the start of conditioning therapy. The first dose is scheduled during this time frame to ensure protein expression at the time of infusion of the donor stem cells as animal models demonstrate that the peak protein expression after injection of a DNA plasmid is between 3 and 14 days. This dose is given prior to the start of conditioning therapy as protein expression may be decreased because of a catabolic state in the patient after the start of conditioning therapy. The second dose of vaccine is scheduled as close to Day 14 after transplant as possible to ensure protein expression and development of a protective immune response at the expected time of the first viremic episodes, which is approximately 30 days after transplant. Finally, doses are scheduled for 60, 90 and 180 days after transplant to help protect against late-onset viremia.

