#### **7.4.3 Analysis of Other Variables**

The maximum grade of aGVHD, maximum cGVHD global score, number of episodes of protocol-defined CMV viremia, and duration of hospitalizations will each be tested using a Kruskal-Wallis test.

Incidence of overall mortality, CMV EOD, grade 3-4 aGVHD, severe cGVHD, grade 3 infections other than CMV, relapse mortality, non-relapse mortality, graft rejection, failure to engraft, and incidence of relapse of primary disease requiring therapy will each be tested using a stratified analysis of the binary response using a CMH test to account for the stratification variables used as part of the randomization. Subjects who discontinue the study without experiencing the event considered in the analysis will be considered as having the event for the statistical analysis.

Number of episodes of protocol-defined CMV viremia [CMV plasma viral load  $\geq 1000$  IU/mL by the Abbott RealTime CMV assay as assessed by the central laboratory] will be compared between treatments using the stratum-adjusted Kruskal-Wallis test, adjusting for donor-recipient relatedness and donor CMV status. To estimate the association between CMV viremia and mortality, a multivariable Cox proportional hazards model will be constructed in a time-dependent manner. The model will be adjusted for the factors used to stratify the randomization. CMV viremia will be treated as a time-dependent variable, starting at the time of the first occurrence of protocol-defined CMV viremia.

The maximum grade of aGVHD, maximum cGVHD global score, and duration of hospitalizations will each be tested using a stratum-adjusted Kruskal-Wallis test adjusting for donor-recipient relatedness and donor CMV serostatus.

The treatment effect on time to engraftment and time to platelet recovery will each be analyzed in a Cox proportional hazards model including the factors used to stratify the randomization.

Immunogenicity analysis will be conducted using the IAS. Descriptive statistics on the raw and log transformed results will be presented by treatment group and collection time point. The Wilcoxon rank sum test will be used to compare treatment groups at each of the time points for immunogenicity assessment for the following:

- Antibody response to gB antigen
- T cell response to viral protein pp65

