## 7.9 Interim Analyses and Early Discontinuation of the Clinical Study

Futility analysis will be conducted during this study. Futility will be monitored based on the effect of ASP0113 on viremia (defined as a CMV plasma viral load  $\geq 1000$  IU/mL as assessed by the central laboratory). It is believed that viremia is a surrogate of treatment effect.

Futility analysis will be performed when the first 100 subjects have been randomized, and every 3 months thereafter until the total enrollment reaches 400 subjects. At each futility analysis, a Bayesian posterior probability that the hazard ratio for viremia of the ASP0113 treatment group to the placebo treatment group will be less than 0.75 will be calculated. The study may stop for futility if this posterior probability is less than 0.15.

Futility analysis will be carried out by an external data analysis group. Sponsor personnel will not have access to unblinded interim analysis data during the study unless the futility criterion is met and the Sponsor needs to make a decision on discontinuing the trial.

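### The SAP's table of viremia within 1 year by death at 1 year has immortal-time bias; name the time-dependent Cox model as the estimate and replace or relabel the table

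*SAP*

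**What the plan says.** SAP 7.4.3.1.1 opens with its purpose: "To estimate the association between CMV viremia and mortality". Two analyses follow under that purpose.

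- **A table.** In it, "subjects in each treatment group will be cross-tabulated by viremia or no viremia within 1 year post-transplant, and by alive or dead" at 1 year. There is no landmark, test or effect measure, and no statement that the table is only descriptive.
- **A model.** "In addition, a multivariable Cox proportional hazards model will be constructed in a time-dependent manner". It is adjusted for the randomization strata, and "CMV viremia will be treated as a time-dependent variable, starting at the time of the first occurrence of protocol-defined CMV viremia". The section then says that the model also includes "all the factors included in the final Cox regression model described earlier in this subsection". No such model appears earlier in 7.4.3.1.1.

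Protocol 7.4.3 and the synopsis plan only the second analysis ("a multivariable Cox proportional hazards model will be constructed in a time-dependent manner"). The table is an addition in the SAP. SAP 6.1.3 lists the association among the exploratory endpoints.

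**The concern.** Viremia within the year is a status that a subject can acquire only by living long enough. The Protocol's Dose Rationale places a protective response "at the expected time of the first viremic episodes, which is approximately 30 days after transplant". Anyone who dies before a first episode is counted as non-viremic, whatever would have happened later. Early deaths therefore collect in the non-viremic column, and the time that viremic subjects had to survive before becoming viremic is credited to viremia. This is immortal-time bias, and it pulls the table towards no association or apparent protection.

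The SAP recognises the mechanism elsewhere. For the viremia endpoint, 7.4.2.1 treats death as a competing event, and 7.4.3.1.2 notes that episode counts depend on length of follow-up. The cross-tabulation has no such safeguard. SAP 7.10.1 also counts unknown survival as death in the crude mortality summary. It does not say whether that rule applies to this table. If it did, early dropouts could enter as non-viremic deaths too.

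What is at stake is how readers interpret the trial's one specified analysis linking viremia to death. The Protocol states of viremia: "It is believed that viremia is a surrogate of treatment effect". A table suggesting that viremia is harmless or protective would be read against that belief.

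**Working it through.** The plan gives no figure for this association, so there is none to reproduce.

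**Inputs from the documents**
- Viremia proportion *v*: 62% placebo, 33% ASP0113 (Protocol 1.3.2.2, phase 2, central laboratory, at least 500 copies/mL). This stands in for the phase 3 threshold of 1000 IU/mL.
- 1-year mortality *m*: 32.4% placebo, 17.5% ASP0113 (Protocol Table 3).
- First viremic episodes at about day 30 (Protocol 2.2.2).

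**Assumptions not in the documents:** the distribution of viremia onset, the shape of the death hazard, and the use of the phase 2 proportions as the probability of viremia in the absence of death.

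**Step 1. Hand calculation with no true effect.** Suppose all viremia starts on day *t* = 45 and the death hazard is constant.

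Deaths before onset: e = 1 − (1 − m)^(t/365).

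Placebo rates: e = 1 − 0.676^(45/365) = 0.047.
- Viremic: v(1 − e) = 0.62 × 0.953 = 0.591. Deaths among them: v(m − e) = 0.62 × 0.277 = 0.172. Risk 29.1%.
- Non-viremic: 1 − 0.591 = 0.409. Deaths among them: (1 − v)m + ve = 0.123 + 0.029 = 0.152. Risk 37.2%.
- Odds ratio: (0.291/0.709) / (0.372/0.628) = 0.69.

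ASP0113 rates: e = 1 − 0.825^(45/365) = 0.023.
- Viremic: 0.33 × 0.977 = 0.322. Deaths: 0.33 × 0.152 = 0.050. Risk 15.5%.
- Non-viremic: 0.678. Deaths: 0.117 + 0.008 = 0.125. Risk 18.4%.
- Odds ratio: (0.155/0.845) / (0.184/0.816) = 0.81.

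With *t* = 30 the same formulas give 0.78 and 0.87. The two arms differ although viremia has no effect in either.

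**Step 2. Simulation with spread-out onset and no true effect.** Onset is lognormal (log-SD 0.6) with median 30, 45 or 60 days. Death is Weibull with shape 0.7 (early-weighted), 1.0 or 1.3 (later-weighted). There are 400,000 subjects per scenario.

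| Rates | Odds ratio from the table |
|---|---|
| Placebo, median 45 days, constant hazard | 0.65 (28.4% vs 37.9% dead) |
| Placebo, all nine scenarios | 0.42 to 0.85 |
| ASP0113, all nine scenarios | 0.58 to 0.91 |

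The lowest values come from late viremia with early deaths, the highest from early viremia with late deaths. In the extreme case of viremia arising at a constant rate all year, the odds ratios are 0.32 (placebo) and 0.42 (ASP0113).

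**Step 3. A real harm.** Take a true hazard ratio of 1.5 for viremia, viremia probability 62%, baseline mortality 28% and constant hazard. The table gives an odds ratio of 0.93 to 1.20 over the three onset medians.

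**Step 4. Alternatives on the same kind of data.** A time-stratified rate ratio with viremia counted only from onset, used as a stand-in for the SAP's time-dependent Cox model, gives 0.98 to 1.02 under no effect and 1.49 to 1.52 when the true value is 1.5. A day-100 landmark table gives an odds ratio of 0.98 to 1.01 under no effect.

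**The case against.** The strongest reply is that the remedy is already in the same section: a Cox model with viremia switched on at first occurrence, as the Protocol planned. That is correct and sets the limit of this point. The table is also exploratory, with no planned test, odds ratio or interval. The odds ratios above are what a reader could compute from it, not planned outputs.

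Three stronger readings are tempting, and the documents do not support them.

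- *The SAP rests its estimate of association on the table.* It lists the table and the Cox model side by side. What is missing is a statement of which one is the estimate.
- *The Cox model cannot be run.* The section names the time-dependent viremia term and the stratification factors, which is enough to fit a model. A natural source for the missing reference also exists: SAP 7.4.3.1 sends 6-month mortality to the method of 7.4.1.2, whose Cox model has treatment, relatedness and donor serostatus. What is unclear is the cross-reference and whether treatment is included.
- *Futility or endpoint conclusions are compromised.* Futility uses the between-arm viremia hazard ratio (Protocol 6.2 and 7.9), and SAP 7.9.2 describes those analyses in the past tense. The key secondary viremia analysis treats death as a competing risk. Neither draws on this table.

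It is also fair to say that the bias can be modest: 0.85 at placebo rates and 0.91 at ASP0113 rates when viremia is early and deaths late.

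The reply does not remove the point that the SAP offers the table for estimation without any caution, and that its direction of error is known.

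**Conclusion.** The concern holds for the cross-tabulation only. With no true effect, the table implies an odds ratio of about 0.4 to 0.9, and a real harm could look like none. The bias also differs between arms, so the per-arm tables could wrongly suggest that vaccination changes the association. The direction follows from the design of the table. The size rests on phase 2 rates and on assumed timing of viremia and death, and should be quoted as a range. The time-dependent Cox model in the same section is not subject to this bias, and the primary, key secondary and futility results are unaffected. This is a worthwhile correction to an exploratory analysis and no threat to the trial's main conclusions.

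**What to change.** In SAP 7.4.3.1.1:

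1. State that the time-dependent Cox model is the estimate of association.
2. Replace the reference to an earlier final Cox model with the terms themselves: time-dependent first protocol-defined viremia, treatment, donor-recipient relatedness and donor CMV serostatus.
3. Replace the cross-tabulation with a landmark table by arm. For example, among subjects alive and under viral-load follow-up at day 100, when weekly testing ends, show viremia by day 100 against death on days 101 to 365. At minimum, keep the existing table but label it as descriptive and not interpretable as an association.

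The cost is a few sentences and one re-programmed table, with no new data. The landmark table leaves out deaths before day 100. At placebo rates with a constant hazard that is 1 − 0.676^(100/365) = 0.102, or 0.102/0.324 = 31% of the year's deaths. It also does not count later viremia as exposure. The Cox model covers both.

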7.4.3.1.2 Number of Episodes of Protocol-defined CMV Viremia

Number of episodes of protocol-defined CMV viremia [CMV plasma viral load ≥ 1000 IU/mL by the Abbott RealTime CMV assay as assessed by the central laboratory] will be compared between treatments using the stratum-adjusted Kruskal-Wallis test, adjusting for donor-recipient relatedness and donor CMV status.

Number of episodes of protocol-defined CMV viremia may be affected by duration of follow-up. Therefore, as a supporting analysis this variable will be compared between

treatments using a log-linear model with treatment, donor-recipient relatedness, and donor serostatus as factors and the log of time of follow-up as a covariate.

7.4.3.2 Duration of Hospitalization, Health Economic, and Quality of Life Variables

Duration of hospitalizations, and days in emergency room, in days per year will be compared between treatments using descriptive statistics.

The number of emergency room visits, and Non-protocol-related physician visits, also will be compared between treatments using descriptive statistics.

The EQ-5D dimensions will be summarized as categorical variables by treatment arm at each visit and at final visit. Change from baseline in the EQ-5D VAS score will be summarized by treatment arm at each visit and at Final visit.

Total FACT-BMT and the corresponding changes from baseline will be summarized by treatment arm at each visit and at Final Visit.

The percent activity impairment due to health from the WPAI: GH and corresponding changes from baseline will be summarized by treatment arm at each visit and at Final Visit.

Treatments will be compared with respect to each of these scales using analysis of covariance (ANCOVA) of change from baseline to final visit with treatment, donor-recipient relatedness, and donor CMV serostatus as factors and baseline value as a covariate.

7.4.3.3 Immunogenicity Variables

T-cell responses to pp65 and gB-specific antibody levels will be summarized by visit and treatment group on the original scale. A plot of each of the immune responses over time by treatment will be produced. The comparisons between treatments will be made at each measurement visit using Wilcoxon rank sum test without adjusting for the multiplicity on the original scale. In addition, each of the immune response variables post baseline on the 10 based log scale will be analyzed using repeated measures model, where the randomization stratum, treatment, time, and treatment by time interaction will be the explanatory variables. The self-consistent sandwich correlation structure will be used. If the test for the time by treatment interaction is significant (p value <0.1) the overall treatment group comparison will not be displayed in the plots.

As an exploratory analysis, the relationship between immunogenicity variables and treatment outcome will be assessed using logistic regression method. The treatment outcome is if subject is free of CMV viremia through one year post-transplant. The optimal cutoff values of the respective immunogenicity variables that will define the treatment outcome will be explored in terms of maximizing the area under the receiver operating characteristic (ROC) curves.

All analyses of immunogenicity variables will be based on the IAS.

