### **4.5 Assignment and Allocation**

At the screening visit, after the Informed Consent Form (ICF) has been signed, the subject will receive a subject number assignment through the IRT for use throughout the study.

Subjects who subsequently meet all inclusion and none of the exclusion criteria will be randomly assigned to receive either ASP0113 or placebo. The randomization to treatment will be equally allocated (i.e., 1:1) and stratified by donor-recipient relatedness and donor CMV serostatus. At least 30% of subjects enrolled will be donor-seronegative.

The IRT vendor will generate the randomization schedule. To obtain the randomized treatment assignment for a subject, the pharmacist or designee will utilize an IRT, which is available 7 days a week, 24 hours a day.

Randomization is to be done after the completion of the screening period, and at least -14 to -3 days prior to the anticipated transplant day (day 0). The first injection must be given within 72 hours prior to the start of conditioning therapy after randomization. After submitting required information about the eligible subject, the drug kit number assignment will be provided.

Study drug assignment will remain blinded to all site staff except the pharmacist and designated staff.

If a subject is randomized but does not receive study drug, the subject number will not be used again. In this instance, the treatment assignment should only be known by the pharmacist and designated staff (i.e., the blind must be maintained as it is with all other subjects).

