3.3 Randomization

At the Screening Visit, after the Informed Consent Form (ICF) has been signed, the subject receives a subject number assignment through the IRT for use throughout the study.

Subjects who subsequently meet all inclusion and none of the exclusion criteria will be randomly assigned to receive either ASP0113 or placebo. The randomization to treatment groups will be equally allocated in a 1:1 ratio and stratified by donor-recipient relatedness and donor CMV serostatus.

The IRT vendor generates the randomization schedule. To obtain the randomized treatment assignment for a subject, the pharmacist or designee utilizes an IRT, which is available 7 days a week, 24 hours a day.

Randomization is done after the completion of the Screening period, and at least 14 to 3 days prior to the anticipated transplant day (Day 0). After submitting required information about the eligible subject, the drug kit number assignment is provided. Study drug assignment remains blinded to all site staff except the pharmacist and designated staff.

Randomization of subjects will continue until approximately 500 subjects have been received at least 1 dose of the study. Subjects who discontinue the study early after receiving the first dose of study drug will not be replaced.

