4 SAMPLE SIZE

In the primary analysis set of a Phase 2 study of the efficacy of ASP0113 in HCT, 7 subjects died and 2 additional subjects experienced CMV EOD out of 40 treated with ASP0113, for

an overall failure rate of 22.5%, while among the placebo subjects 11 subjects died and 1 additional subject experienced CMV EOD out of 34, for an overall failure rate of 35.3%.

To detect the estimated difference in mortality and CMV EOD from the phase 2 study (35.3% vs. 22.5%), the study needs a sample size of at least 424 (212 per arm) to have 80% power at the 2-sided significance level of 0.050. A trial of size 500 (250 per arm) is expected to have 86% power for the composite endpoint.

All calculations used nQuery Advisor 7.0, procedure PPT1 [2 group continuity corrected χ^2 test of equal proportions (odds ratio = 1) (equal n's)] with the assumptions described above.

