7 STATISTICAL METHODOLOGY

7.1 General Considerations

All statistical analyses and summary information will be generated according to this statistical analysis plan. Any analytical deviations from this plan will be documented in the clinical study report. All numerical rounding should be performed at the end of calculations. The p-values will be displayed with 3 significant digits. Statistical significance will be determined prior to rounding the p-value.

For continuous variables, descriptive statistics will include the number of subjects (n), mean, standard deviation (SD), median, minimum and maximum. Frequencies and percentages will be displayed for categorical data. Percentages by categories will be based on the number of subjects with no missing data (i.e., will add up to 100%).

The analyses with the randomization stratification factors, donor-recipient relatedness (Related/Non-related) and donor CMV serostatus (Positive/Negative), that are used in the analyses will be based on the data from IRT.

All statistical comparisons will be made using 2-sided tests at the $\alpha=0.05$ significance level unless specifically stated otherwise.

The analysis day will be calculated from the day of transplantation day (efficacy analysis day 0). Further details on data handling conventions are specified in Section [7.10](#) For patients who took study drug but did not receive HCT, the analysis day will be calculated from the first study drug injection day (safety analysis day 1).

This SAP includes the plan for data analysis for the primary study period (i.e., 1-year post transplantation) which is defined as data collected through day 380 (=365+14+1 day) from transplantation. The long-term follow-up period is not covered by this SAP and will be managed in a separate SAP.

All data processing, summarization, and analyses will be performed using SAS[®] Version 9.4 or higher on Unix.

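### The per-visit immunogenicity tests ignore the randomisation strata; a stratified Wilcoxon test would avoid a possible loss of power at almost no cost

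*SAP*

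**What the plan says.** SAP 7.4.3.3 has the arm comparisons "made at each measurement visit using Wilcoxon rank sum test", on the original scale and with no multiplicity adjustment. Protocol 7.4.3 agrees: "The Wilcoxon rank sum test will be used to compare treatment groups at each of the time points for immunogenicity assessment". Neither sentence names a stratification factor.

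SAP 3.3 describes allocation as "equally allocated in a 1:1 ratio and stratified by donor-recipient relatedness and donor CMV serostatus", which gives four strata. Protocol 4.5 adds a quota: "At least 30% of subjects enrolled will be donor-seronegative". No block size is stated in either document.

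Elsewhere the SAP carries these two factors into its comparisons: the CMH test for the primary endpoint (7.4.1.1), the Cox models (7.4.1.2, 7.4.2.1), the ANCOVA for quality of life (7.4.3.2), and the repeated measures model for the immune responses, which follows the Wilcoxon sentence in 7.4.3.3. Its only other rank test is for the number of viremia episodes (7.4.3.1.2), to be "compared between treatments using the stratum-adjusted Kruskal-Wallis test, adjusting for donor-recipient relatedness and donor CMV status". With two arms, that is a stratified Wilcoxon test.

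**The concern.** A plain two-sample Wilcoxon test ranks all subjects together, so any difference in response between strata is counted as noise. A stratified test ranks within strata and removes it. It is plausible that donor CMV serostatus affects the recipient's CMV immunity after transplant, in which case the plain test gives up power for nothing. If the arms are also balanced within strata, it uses too large a variance and rejects less often than its nominal level.

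The visit tests are the only visit-level inference specified for immunogenicity. The repeated measures model is on the log10 scale and no per-visit contrasts from it are stated. If its time-by-treatment interaction has p below 0.1, the overall comparison is left out of the plots.

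**Working it through.** **The plan's own figure.** No power is stated for immunogenicity. The only power statement, in SAP Section 4, is "A trial of size 500 (250 per arm) is expected to have 86% power for the composite endpoint". The continuity-corrected formula with 35.3% and 22.5% gives 212 per arm for 80% power, as stated, and 86.6% at 250 per arm. It concerns the primary endpoint and is used here only for the total of 500.

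**Inputs from the documents.** 500 subjects, 1:1; four strata; donor-seronegative share set at its 30% floor; two-sided 0.05 (SAP 7.1).

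**Assumptions not in the documents.** 40% related donors; permuted blocks of four within stratum; normal responses with within-stratum SD 1; shift *a* for donor serostatus and *b* for relatedness; a treatment shift giving the stratified test about 80% power:

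(1.96 + 0.8416) × 2/√500 × √(π/3) = 0.256 SD.

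**Variance explained by strata.** v = a²(0.3 × 0.7) + b²(0.4 × 0.6), and the share is v/(1 + v). With a = 1 and b = 0.4, v = 0.21 + 0.0384 = 0.2484 and the share is 0.2484/1.2484 = 20%.

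**Simulated results, 500 analysed, plain vs stratified Wilcoxon:**

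| a, b | Share | Type I error | Power |
|---|---|---|---|
| 0, 0 | 0% | 4.6% vs 4.7% | 80.3% vs 79.8% |
| 0.25, 0.1 | 1.5% | 4.9% vs 5.3% | 80.3% vs 80.3% |
| 0.5, 0.2 | 6% | 4.2% vs 5.0% | 78.4% vs 79.9% |
| 1, 0.4 | 20% | 3.1% vs 5.2% | 73.3% vs 80.1% |
| 1.5, 0.5 | 35% | 1.2% vs 4.4% | 64.4% vs 79.8% |

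The 6% and 20% rows use 10,000 trials and the others 4,000, so the standard error is at most about 0.6 points for power and 0.35 points for type I error.

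**Hand check.** With arms balanced within strata, the plain test divides by √(1 + v) where 1 would be right, so its effective critical value is 1.96√(1 + v). At v = 0.2484 this is 1.96 × 1.117 = 2.19. Type I error is then 2[1 − Φ(2.19)] = 2.9%, and power is Φ(2.80 − 2.19) = Φ(0.61) = 73%. Both agree with the 20% row.

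**Fewer samples.** With 40% of the 500 missing at random (about 300 tested) and the treatment shift rescaled to 0.331 SD, the results are:
- 6% share: power 77.5% vs 78.9%, type I error 4.9% vs 5.6%.
- 20% share: power 71.2% vs 79.5%, type I error 4.0% vs 4.8%.
- 35% share: power 62.5% vs 78.9%, type I error 2.3% vs 4.4%.

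**Exact balance among 300 tested.** A separate simulation had a 65% seropositive-donor share, exact 1:1 balance within strata and a shift of 0.333 SD. Power was 79% vs 80% at a 5% share, 73% vs 79% at 15%, 72% vs 81% at 20% and 65% vs 79% at 30%. Type I error was 2.6% vs 4.7% at 20% and 1.5% vs 4.8% at 30%.

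**No balance by design.** Under simple randomisation at a 20% share, type I error is 5.05% vs 5.04%, but power is still 70.5% vs 79.1%. The power loss does not depend on balance; the conservatism does.

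**The case against.** The strongest reply is that little hangs on these tests. Immunogenicity is exploratory (Protocol 2.3.3), the visit tests are openly unadjusted for multiplicity, any error is in the conservative direction, and no primary or key secondary inference is touched. A stratum-adjusted model of the same variables is already planned, and its interaction term would allow adjusted visit contrasts. All of this stands and sets the materiality. It does not remove the point, because those contrasts are not specified. Phase 2 also shows that the two approaches can read differently: for gB antibody, the Wilcoxon test gave P = 0.009 at day 365 while the repeated measures analysis gave P = 0.749 (Protocol 1.3.2.2).

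A second reply is that the SAP follows the protocol's named test, and that phase 2 used the same test per visit, so keeping it preserves comparability. That is a fair reason to keep it as a supportive analysis.

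A third is that the stratum effect is unknown and unlikely to be uniform. All recipients have gB antibody before transplant (Protocol 5.3.7), and V2 samples are taken before transplant, when the graft cannot have acted. This stands: one variance share should not be read across both assays and all visits.

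A reader might also cite the subgroup analysis by donor T-cell immunity in Protocol 7.4.1.3 as proof that the plan expects the strata to drive immune response. It does not show that. It concerns the primary endpoint, depends on enough donors enrolling, and is absent from the subgroup list in SAP 7.4.1.4. The donor sub-study samples only seropositive donors, so it does not contrast serostatus.

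**Conclusion.** The point holds as a low-stakes improvement. If the strata predict the response, the plain Wilcoxon test loses about 1 to 2 points of power at a 5 to 6% variance share, 7 to 9 points at 20% and about 15 points at 30 to 35%. With no stratum effect it loses nothing. The shares are assumed, and the effect size was chosen to give about 80% power.

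A reader might infer that the true error rate is simply below 5%. The documents do not support that as a fact. It needs both a stratum effect and within-stratum balance among the samples tested. The documents say stratified, not blocked. T-cell samples are not collected at low lymphocyte counts (SAP 6.1.4), and the analysis set requires a post-transplant measurement (SAP 5.7), so balance at a visit is not assured. Nor do the documents support a claim that a real immune response will be missed: that depends on the unknown stratum effect. There is no inflation of type I error.

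**What to change.** In SAP 7.4.3.3, replace the plain test at each post-transplant visit with the stratum-adjusted (van Elteren) Wilcoxon test, using donor-recipient relatedness and donor CMV serostatus from the IRT, as SAP 7.1 already requires for stratified analyses. Record the departure from Protocol 7.4.3 in SAP Section 8 with the reason. If comparability with phase 2 is wanted, keep the unstratified test as a supportive analysis.

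The cost is a short text change, a logged deviation and the same kind of procedure already needed for the episode counts. No new data are required, and in the simulations power is essentially unchanged when the strata do not matter. The change should be made before unblinding.
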